The national public health opioid crisis has disproportionately burdened rural white populations, and disproportionately burdened American Indian populations. Therefore, the Cherokee Nation (CN) and Emory University public health scientists have designed an opioid prevention trial to be conducted in at-risk rural communities in the CN (in northeast Oklahoma) with white and American Indian adolescents and young adults. Our goal is to implement and evaluate a theory-based, integrated multi-level community intervention designed to prevent the onset and escalation of opioid and other drug misuse. We propose a community randomized trial building directly on the success of our most recent previous trial, which demonstrated that our intervention effectively reduced alcohol and other drug use among American Indian and other youth living within the CN. Two distinct intervention approaches—community organizing as implemented in our established CMCA intervention protocol, and universal school-based brief intervention and referral as implemented in our established CONNECT intervention protocol—will be expanded and integrated to further enhance effects in preventing and reducing opioid misuse. The CMCA and CONNECT interventions were originally designed to target adolescent alcohol use, but nevertheless showed significant beneficial effects also on use of other drugs, including prescription drug misuse. The proposed study will: (1) further improve the design of the interventions with increased focus on opioids, (2) test the expanded, integrated versions in a community randomized trial, and (3) design and test new systems for sustained implementation within existing structures of the Cherokee Nation. Building upon the extant prevention science evidence, our study will respond to a gap in evidence concerning opioid misuse prevention among at-risk adolescents transitioning to young adulthood among American Indian and other rural youth. Our previous trial, conducted in partnership with the Cherokee Nation, ended with youth attaining age 18; the proposed new trial will additionally advance the science regarding strategies to engage young adults as they transition beyond high school.

II. Methods and Study Population

[figure not shown]
Sample

Sixteen to twenty-four high schools and surrounding towns within the 14-county Cherokee Nation reservation in northeast Oklahoma will be purposively selected based on school and community characteristics (e.g., size of high school, distance between towns, existing prevention program), stratified by risk profile, and randomly assigned to study condition: (1) preventive intervention or (2) delay-program control. In-person meetings will be conducted with project leadership and school leadership (school district superintendents and high school principals). PIs will present study details and invite the school leadership to participate in the study and to sign a cooperative agreement form. If the high school within a selected town refuses to participate, a replacement town will be selected from within risk strata. Given our recruitment history, we anticipate a very high participation rate—our recent prevention research project with the Cherokee Nation resulted in a 100% school participation rate.

Prevention Program Overview

School district superintendents and high school principals will be asked to sign cooperative agreement forms to participate in the study. As with our previous school-based projects, school-based screening, brief intervention and referral (CONNECT program), conducted by Cherokee Nation Behavioral Health counselors, will be treated as part of the participating schools' prevention programs. According to Oklahoma State statute (Stat. tit. 63 § 2602. Right of self-consent) a minor may consent to services for the prevention, diagnosis and treatment of drug and substance or alcohol abuse treatment. In addition, the Oklahoma Department of Public Health trains school nurses to provide health education and counseling to help prevent tobacco use, alcohol use, substance abuse, and other health related issues. The CONNECT school-based prevention program is consistent with the laws and standards of practice in Oklahoma. Cherokee Nation Behavioral Health (CNBH) youth services provides a central hub connecting youth and their families to programs, resources and services. The CNBH CONNECT coaches will introduce and support the CONNECT program. Each semester, a computer-based CONNECT screening and brief intervention will be implemented universally, to reduce potential stigma and to reinforce drug-free norms among all students. Universal screening avoids contributing to harmful, negative stereotypes likely to result from singling out students. The computer-based universal screening and brief intervention will be supported by either one or two Connect Coaches. As originally planned, follow-up of moderate to high-risk youth will be conducted by a Connect Coach through Zoom, other electronic communication, or in-person visits, with referral to Cherokee Nation or community services if deemed necessary.

The Computerized Intervention Authoring System (CIAS), an NIH-funded non-commercial research resource that allows development of interactive and tailored digital health interventions, will be used to develop the computer-based screening and brief intervention. The CIAS system was previously used to develop and test a computer-based alcohol and marijuana brief intervention with motivational interviewing (CBI) for school-based health centers and was found to be as effective as a nurse practitioner-delivered brief intervention (NBI) ([name] et al., 2021; R01DA036604, PI [name]). There were no significant differences between NBI and CBI on any outcomes, including marijuana use, marijuana-specific problems, alcohol use, binge drinking, alcohol-specific problems. [name] has given us full access and permission to adapt the program for our needs, facilitating rapid development of an effective computerized version of screening and brief intervention. Students will be given a personal CONNECT ID number to access the computer-based brief intervention on a project computer, which will be set up in a private location with the schools. No personal identifying information will be entered into the computer or brief intervention program. A flow chart showing the implementation details is below. This process allows all collected CONNECT screening data to be stored in a deidentified manner. The school personnel will not be able to access any data entered into the CIAS system. We will work with each school to troubleshoot any implementation/logistic problems throughout the intervention period.

The community-level intervention Communities Mobilizing for Change and Action (CMCA) will involve educating and organizing of adult volunteers and consent will be assumed by their participation. We will provide trainings and tools, including Family Action Kits, to support local families, community organizations and citizens, including information on national and local opioid and other drug use, evidence-based policies, programs and practices, and how to motivate and create family and local action for drug prevention.

The intervention will be further enhanced by including Cherokee Nation award-winning multi-media suicide prevention strategies adapted for drug use prevention.

The evaluation of the prevention programs will be accomplished through self-report surveys of a cohort of high school students followed over three years, from grade 10 (ages 15-17) to the year following high school graduation (ages 18-20). A pilot survey will be administered in the study schools using all approved protocols in grade 9. The main outcome analysis will include baseline (fall of 10th grade) through spring of 12th grade surveys. A secondary outcome analysis will include the six-month follow-up survey conducted six months post on-time high school graduation.

Recruitment Procedures

All 10th grade students enrolled in the participating study high schools will be eligible to participate in the study. As a universal preventive intervention, and given the need for a community-wide representative sample, there are no exclusionary criteria. Beginning in 10th grade, a cohort of high school students will be asked to participate in a brief, 20-30-minute, web-based survey on health behaviors two times per year. The survey will be administered using REDCap or Qualtrics on cellular-connected project tablets and implemented during homeroom, a class period, lunch period, or at

another time convenient to each school and participant. All data will be encrypted as soon as it is entered and transmitted to a central server at Emory University. No school personnel will be involved in any survey administration tasks, avoiding any potential risks and biases that could accrue from the involvement of school personnel in survey administration.

All 10th grade students in all participating high schools will be recruited. Participating schools will provide the researchers with a list of the most current home addresses and telephone numbers for all students in the participating high schools. Parent consent letters will be sent home by Emory University and the Cherokee Nation, describing the study and its importance and providing a toll-free and local telephone number that parents/guardians can call with questions or concerns. In-person visits will be made when requested or if the parent is unavailable via phone. Parents will be asked to respond by returning an addressed postage-paid postcard or calling Cherokee Nation Behavioral Health using toll-free telephone numbers, if they refuse permission for their son or daughter to participate. Also, each adolescent/young adult participant will be given the opportunity to decide not to participate, and may withdraw their participation at any time. Students will be provided \$5 for each biannual survey implemented within schools. For the six-month follow-up survey, planned for Fall 2024, administered outside of school, a \$50 electronic Visa or gift card will be provided. A number of steps will be taken to maximize participation and retention rates. The fact that the intervention and assessments proposed in this application will be endorsed by the Cherokee Nation and school leadership at the participating high schools will help maximize participation rates. Youth will receive reminders and compensation for their time. For youth who are missing from school during survey administrations, tactics to reach them for follow-up surveys may include emailing and texting to ask how they are, update social media, email, phone and other contact information, and reminding them about an upcoming survey. We will use procedures for tracking and follow-up surveys as we implemented in a long-term follow-up of a cohort of youth in Chicago, including secure internet and in-person survey administration options. Although some attrition is anticipated, a substantial proportion of the students recruited at baseline are expected to be retained in the study. In our previous prevention trial in the Cherokee Nation, we maintained over 80% participation across the three-year study.

Our recruitment and retention protocol requires careful planning and treating school leadership, parents and study participants with respect and courtesy. Our previous trials demonstrate this has worked well—we have consistently been able to recruit a substantial percentage of the sample and have experienced few refusals. As with all field studies, recruiting students and parents/guardians in this fashion necessarily introduces potential selection bias because those who participate may be systematically different from those who decline. However, maintaining a respectable baseline participation rate, conducting descriptive analyses to determine whether the final sample is representative of the school demographically and to ensure comparability on relevant characteristics between communities, and weighting to adjust for nonresponse helps offset the effects of selection bias. Also, bias will be somewhat further reduced by providing financial incentives and maintaining direct contact with schools, parents and students.

Measures

The Youth Experiences Survey is attached. It will be used to collect data from youth participants to assess substance use and related risks/harms, perceived availability of opioids and other drugs, knowledge and perceptions of consequences, values and beliefs about substance use, social normative beliefs around substance use, social skills and social support.

Each participant will be asked to complete a Contact Information Form during the final school-based survey in Spring 2024. The contact form will be a scannable paper form, separate from the tablet-based student survey, and students will be provided \$5. The form asks about contact information to help us

maintain contact and reach participants for the follow-up survey. We will ask youth to provide phone numbers, email address, and home address. The Contact Information Form is attached. Mid-summer we will contact participants via text, call, or email to ask for confirmation of contact information. A \$10 electronic Visa or gift card will be provided for confirming contact information.

III. Risk/Benefits

The data-gathering requirements and intervention activities of the proposed research pose no more than minimal risk to participants. The surveys will be designed to be of limited distress, although a student may be uncomfortable answering certain questions. The surveys are short—average completion time is expected to be 20-30 minutes. Participants will be reminded at the beginning of the survey that they are free to skip any questions or to stop the survey at any time. Our confidence in terms of the measures to be used is based on many years of experience in using these surveys. Moreover, students have reported a high level of comfort with the surveys and assessments in the past. Although rare, there is a possibility for the surveys to produce some stress or frustration, which will be carefully monitored. Thus, at most, participants may find these assessments boring, annoying, or frustrating.

There is potential for significant direct benefits of this project to participating adolescents and young adults; the evidence-based interventions are expected to improve several outcomes under study, such as preventing the onset and escalation of drug use and related risks/harms. The control sites will be offered the intervention materials at the end of the study, as well as the opportunity for teacher and staff trainings provided Cherokee Nation Behavioral Health during the active study phased (e.g., bullying prevention training).

The minimal risk of a breach of confidentiality, plus possible discomfort that may accompany some behavioral change efforts, is easily outweighed by the likely benefits.

IV. Data Security/Monitoring

Data collectors will be professional staff with training in Human Subjects Research. They will be thoroughly trained in the principles of the study and use of the survey methods. They will also be qualified to interact with adolescents, parents, and school administrators. Drs. [name] and [name] will coordinate and train on collection of survey data. An Evaluation Field Supervisor will oversee all field activities, including administration of assent forms, coordination with schools and teachers, and administration of assessments. The tracking and assessment databases will be linked by arbitrarily-assigned study numbers (not school ID or other such numbers) to ensure identifying information is not contained in the assessment databases. Data collected for the study will be transmitted immediately via cellular-connected tablets using REDCap or Qualtrics to the Emory University server where checks will be run for data consistency and quality. It is important to note that the schools will not obtain or maintain any individual-level survey results and research staff will not retain any identifying information; thus there will be no way to link names with survey results. Processes are in place to generate de-identified databases and statistical programs for analyses.

Prior to any member of the research staff initiating contact with research participants, they will be trained in the following areas: 1) Protecting human study volunteers in research in accordance with Emory and Cherokee Nation IRB requirements; 2) Understanding the project grant (background, application, and aims); 3) Demonstrated understanding of data collection forms; 4) Understanding how all forms are filed, both electronic and material (i.e. exact location, computer drive, folders, and which

electronic files need to be password protected); 5) Understanding which type of events need to be reported and the process of reporting (e.g., emotional reports related to incidence of victimization or violence, adverse events reporting, active suicidal/homicidal ideation, releasing information, etc); and 6) Survey and follow-up protocols. Training tasks will be organized by a checklist which will be completed during orientation. Prevention of minor adverse events will include the following. Participants will be acclimated to the study in the school, which will be familiar to them. They will be given time to relax and ask questions. They will also be assured that, if at any time they experience any emotional discomfort, they may request a break or ask to be discontinued from the study. The investigators have been conducting both clinical and research work with adolescents for many years. If a student reveals any abusive experiences, the interviewer will be required to report it to the school or a local authority. The PIs, in consultation with the IRBs, will determine if they are mandated to report the incident to an appropriate professional or authority.

Protections relevant to children.

We believe that study participation of adolescents and young adults, ages 15-20, involves no more than minimal risk. All of the interventions to be provided have been shown in experimental trials to benefit adolescents. Most have beneficial effects on drug use. Participation in surveys poses, at most, minor risks of discomfort.

Data Collection and Management Procedures.

We will collect data from youth to assess risk and protective factors, substance use and related harms. Age ranges of the youth will be from 15 to 20. Students will complete a short (20-30-minute) survey each semester within their homeroom, selected class period, or lunch period or on their own time through electronic survey distribution and once again approximately six months following graduation to monitor influences and outcomes. When in-school survey administration is not feasible students will be asked to participate in a private location through an electronic survey link. On average, each student will provide approximately seven data points throughout the project.

Data collectors will be professional staff with training in Human Subjects Research. They will be thoroughly trained in the principles of the study and use of the survey methods. They will also be qualified to interact with adolescents, parents, and school administrators. Drs. [name] and [name] will coordinate and train on collection of survey data. An Evaluation Field Supervisor, under the supervision of the PIs, will oversee all field activities, including administration of assent forms, coordination with schools and teachers, and administration of assessments. The tracking and assessment databases will be linked by arbitrarily-assigned study numbers (not school ID or other such numbers) to ensure identifying information is not contained in the assessment databases. Data collected for the study will be transmitted immediately via cellular-connected tablets using REDCap or Qualtrics to the Emory University server where checks will be run for data consistency and quality. It is important to note that the schools will not obtain or maintain any individual-level survey results and research staff will not retain any identifying information; thus there will be no way to link names with survey results. Processes are in place to generate de-identified databases and statistical programs for analyses.

The deidentified data collected within the CIAS CONNECT system will reside on secure servers at Michigan State University. Only the PI, the research project manager and the CONNECT coaches will have access to the link list of CONNECT ID to participant name.

Confidentiality

NIH's Certificate of Confidentiality (CoC) policy automatically issues a CoC for any NIH-funded projects using identifiable, sensitive information. Further information is included in the Confidentiality Certificate section.

V. Data Analysis

Throughout the study, age ranges of the students will be from 15 to 20. Students will complete a short (20-30-minute) survey each semester within their homeroom, selected class period, or lunch period or on their own time through electronic survey distribution and once again approximately six months following graduation to monitor influences and outcomes. When in-school survey administration is not feasible students will be asked to participate in a private location through an electronic survey link. On average, each student will provide approximately seven data points throughout the project, so we can analyze trends over time in the onset and escalation of risk and protective factors and drug use outcomes.

We will analyze the effects of the CMCA and CONNECT interventions on proximal outcomes (e.g., perceived availability of drugs, social normative beliefs, social support, self-efficacy, and normative estimates of peer drug use) and on distal outcomes of opioid and other drug use (e.g., prescription opioids without a doctor telling you to take them, marijuana use, alcohol use). The trial consists of "doubly repeated" measures--repeated measures nested within each student, plus students are nested within schools. Any statistical analysis that ignores lack of independence due to nesting will be subject to inflated type-1 errors. To account for both the clustering effect of students nested within schools and repeated measures nested within student, intervention effects on proximal and drug use outcomes will be estimated with generalized linear mixed models.

As part of our strategy to follow students into the first year after their expected graduation, we will employ extensive tracking procedures to maintain a high response rate across study waves. There may still exist students who miss survey administrations or who are lost to follow-up. As in our previous Cherokee Nation prevention trial, we will use multiple imputation to account for non-response over time and potential attrition. All available outcomes data will be used to impute missing outcome data from those with missing survey waves.

VI. Dissemination

Sharing of the data generated by this project is key to the project, especially if the intervention is successful. We anticipate that we will present on the intervention and evaluation process in the second year and at least annually on data collected after the second year when sufficient baseline data are collected. Sharing of the findings will involve a primary paper describing the study outcomes and papers that describes the study design and intervention implementation details, as well as submitting to lead workshops on the intervention approaches at relevant national meetings and conferences.

De-identified data for additional analyses will be available to outside individuals through contacting the PI and with approval of the Cherokee Nation Institutional Review Board. Access to data will not be possible until the publication and release of the main outcome papers. After this, we will institute a concept plan process where internal study staff first have the availability to write primary papers or give presentations on particular topics. If outside individuals then wish to analyze data, we will welcome this collaboration. Contact information for the PI will be listed on all manuscripts and publications as a means to access the data. We will abide by the Steering Committee's data and resource policy,

consistent with the relevant NIH policies, laws and regulations and with approval from the Cherokee Nation Institutional Review Board.

The current versions of the CMCA Handbook and CONNECT materials are available through the Emory Prevention Research Center's website (<http://web1.sph.emory.edu/eprc/research/cmca-connect.html>). We plan to update this website and the materials as we expand the interventions to address substance use.

Clinicaltrials.gov: We will ensure that clinical trial under the award are registered and results information is submitted to ClinicalTrials.gov as outlined in the policy and according to the specific timelines stated in the policy; informed consent documents for the clinical trial will include a specific statement relating to posting of clinical trial information at ClinicalTrials.gov; and Emory University has an internal policy in place and of Office of Research Compliance to ensure that clinical trials registration and results reporting occur in compliance with policy requirements.

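### Schools are stratified by risk profile before randomisation, but the mixed models do not mention the strata; the standard error is overstated if allocation is balanced, the strata predict the contrast and between-school variance is modelled

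*Combined protocol and SAP*

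**What the plan says.** Section II (Sample): "Sixteen to twenty-four high schools and surrounding towns within the 14-county Cherokee Nation reservation in northeast Oklahoma will be purposively selected". The schools are then "stratified by risk profile, and randomly assigned to study condition: (1) preventive intervention or (2) delay-program control". If a school refuses, "a replacement town will be selected from within risk strata". The strata are therefore a working part of the design. The natural reading is randomisation within strata, although the sentence also allows stratified selection followed by unrestricted randomisation.

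Section V (Data Analysis) names the structure that the model is built for: "To account for both the clustering effect of students nested within schools and repeated measures nested within student". The method chosen for this purpose is given in the same sentence: "intervention effects on proximal and drug use outcomes will be estimated with generalized linear mixed models". The risk strata are not mentioned. Nor are covariates, the link, the contrast, or a reference distribution or degrees of freedom (df).

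Two other places bear on this:
- On the analysis window: "The main outcome analysis will include baseline (fall of 10th grade) through spring of 12th grade surveys". Section V adds that the repeated surveys are collected "so we can analyze trends over time in the onset and escalation of risk and protective factors and drug use outcomes". Both lean towards a change or arm-by-time contrast, but neither fixes one.
- Recruitment Procedures proposes descriptive analyses "to ensure comparability on relevant characteristics between communities, and weighting to adjust for nonresponse helps offset the effects of selection bias". These do not put the strata into the outcome model.

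**The concern.** Balancing strata across arms removes stratum differences from the true sampling error of the arm comparison. A model without the strata leaves those differences in its estimate of between-school variance, so the reported SE is larger than the real one. With 16 to 24 clusters, precision is limited by the number of schools. The stake is lost power and intervals wider than the design requires. Section V warns about inflated type I error from ignored nesting but does not discuss this opposite error.

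**Working it through.** The available text gives no power, alpha, intraclass correlation (ICC) or outcome rate, so there is no stated figure to reproduce. The check uses school-level summaries of the analysed contrast.

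**Inputs.** From section II: m = 16 or 24 schools, two arms. Assumed: 1:1 balance within S equal strata, S = 2 to 4, two-sided 5% test, and a share r = 10% or 20% of the school-level contrast variance explained by the strata.

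**Step 1: SE when strata are omitted.** Reported/true SE (root mean square) = sqrt(1 + [m/(m-2)] x r/(1-r)).
- r = 0.10: m = 16, sqrt(1 + 1.143 x 0.111) = 1.06; m = 24, sqrt(1 + 1.091 x 0.111) = 1.06.
- r = 0.20: m = 16, sqrt(1 + 1.143 x 0.25) = 1.13; m = 24, sqrt(1 + 1.091 x 0.25) = 1.13.
- r = 0: 1.00.

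Simulations that use the mean SE give slightly lower values: about 1.03-1.06 and 1.10-1.13.

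**Step 2: test size and power, t on m-2 df (simulation).**

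| Stratum share | Null rejection, strata omitted | Power, if 80% with strata |
|---|---|---|
| 0 | about 5% | no loss |
| 10% | 3.8-4.0% | 76-79% |
| 20% | 2.6-3.0% | 71-74% |

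With strata included and t on m-S-1 df, null rejection is about 5%.

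**Step 3: normal reference.** The SE ratio does not change, but the test does. With non-prognostic strata omitted, null rejection is 7.0% (m = 16) or 6.3% (m = 24). At r = 10% it is about 5-6%, so an overstated SE need not make the test conservative. With 2-4 strata in the model it is 7.2-7.6% or 6.3-6.5%.

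**Step 4: change contrast with student noise.** Assume 60 students per school and a change ICC of 0.01 or 0.02, with total variance 1. The variance of a school's mean change is ICC + (1-ICC)/60.
- ICC 0.01: 0.0100 + 0.0165; true school share 0.0100/0.0265 = 0.377.
- ICC 0.02: 0.0200 + 0.0163; true school share 0.0200/0.0363 = 0.551.

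If the strata explain 10% of true school change variance, the effective r is 0.038 or 0.055, and Step 1 gives 1.02-1.03. At 20%, r is 0.075 or 0.110, giving 1.04-1.07.

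**Step 5: change contrast with random intercepts only.** School and student intercepts cancel from change, so school-level change variance is missing from the SE. Reported/true SE is roughly sqrt{(1/60) / [(1-r) x ICC + (1-ICC)/60]}.
- ICC 0.01: r = 0.10, sqrt(0.0167/0.0255) = 0.81; r = 0.20, 0.82.
- ICC 0.02: r = 0.10, sqrt(0.0167/0.0343) = 0.70; r = 0.20, 0.72.

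Here the SE is too small. Simulation gave 0.69-0.83, with null rejection of 7.6-14.9%.

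**Step 6: unrestricted randomisation.** With strata omitted, the SE ratio is 0.99-1.00 and t-based rejection 4.7-5.2%.

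**The case against.** The strongest case against runs as follows.

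- **Silence is not exclusion.** Section V is a short summary that lists no fixed effects at all. A reader might infer that the sponsor has decided to leave the strata out; the text does not support that. It supports only that the plan does not say. A figure directly above the Sample section is not shown and might describe the strata. That limits any claim about how many strata there are, but it does not put them into the model in section V.
- **The direction is not guaranteed.** A reader might infer that omitting the strata always overstates the SE. Step 5 shows the opposite for an arm-by-time contrast with only school and student intercepts, a model that section V's wording permits. This stands, and it is why modelling the between-school variance of the contrast is a condition.
- **The reference distribution does not alter the SE.** It is tempting to say that the SE is overstated because a t test is used. The choice of t or normal affects only whether the test is conservative.
- **Harm may be nil.** Stable stratum differences cancel from a change contrast. For a baseline-adjusted contrast, the overstatement nearly vanishes if strata with higher levels change less: -2 to +1% at a 10% share and 0 to 3% at 20%. The documents do not give the sign. This also stands.
- **The stratum term alone can leave rejection above 5%.** With a normal reference it does (Step 3), so the term and the df method must be specified together.

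**Conclusion.** The concern holds as a conditional one. The plan stratifies schools by risk, apparently randomises within strata, and does not carry the strata into the analysis model. Omission overstates the SE when allocation is balanced within strata, the strata predict the analysed contrast, and the model captures the between-school variance of that contrast. The size is then about 3-6% at a 10% stratum share and 11-13% at 20%, or about 2-3% and 4-7% for a change contrast with the assumed student noise. With a t reference and the larger SE figures, null rejection is near 4% and 3%.

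These strengths, the 60 students per school and the change ICCs are assumptions. The calculations treat school summaries as normal, so they are approximate for a binary model. Under these conditions and a t reference, the consequence is lost power. No stated figure is contradicted. This is a cheap improvement of moderate priority.

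**What to change.** In section II, state whether schools are randomised within risk strata, how many strata there are, and whether arms are balanced within each.

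If randomisation is within strata, state in section V that:
- risk stratum enters each mixed model, for proximal and drug use outcomes, as a fixed effect;
- if the effect is arm-by-time, stratum-by-time terms and a school-by-time random effect are included, because a stratum main effect alone would not help there;
- inference uses a school-level small-sample df, about schools - strata - 1, carried through the pooling of the multiple imputations;
- the estimation method is named. In a binary check of a level contrast without repeated waves, maximum likelihood with strata still rejected 6-7% on t df, against about 5% for REML pseudo-likelihood. The repeated-wave model was not checked in this way.

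No new data are needed. The cost is (strata - 1) school-level df. From the noncentral t, for non-prognostic strata with balanced allocation and 80% power without them, 2, 3 or 4 strata cost 0.47, 1.02 or 1.69 power points at 16 schools (13, 12 or 11 df). At 24 schools they cost 0.18, 0.37 or 0.59 (21, 20 or 19 df).

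Adjustment is optional in two cases. If the strata are matched pairs, the cost is 6.6 points at 16 schools (7 df) and 3.9 at 24 (11 df). If the strata served only for selection, non-prognostic strata cost about 2-4 points with 2-3 strata, and about 10 with 4 strata in 16 schools.
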